7.3.3 Subject Withdrawal Criteria

A subject may withdraw from the study at any time for any reason.

A subject will be withdrawn from the study if his/her safety or well-being is determined to be at risk. Withdrawal will be made at the discretion of the investigator or at the subject's request.

A subject must withdraw from the study for any of the following reasons:

- The subject or legal representative withdraws consent
- There is a significant protocol violation as determined by the Sponsor or medical monitor.

A subject may be withdrawn from the study for any of the following reasons:

- Lost to follow-up
- Investigator discretion

Withdrawal is permanent; after a subject has been withdrawn, he/she will not be allowed to enroll again.

If a subject is withdrawn from the study for any reason, the EOS or Early Termination procedures (Visit 3/Month 2) should be completed and any outstanding data and study device should be collected. Data, including the date and primary reason for withdrawal, must be documented on the EOS case report form (CRF) and source document.

If a subject withdraws from the study at any time due to an AE, the reason for withdrawal, the nature of the AE, and its clinical course must be fully documented. The investigator must strive to follow the subject until the AE has resolved, become clinically insignificant, is stabilized, or the subject is lost to follow-up. For any SAE, follow procedures provided in Section 7.9.7.

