7.9 Assessment of Safety

7.9.1 Safety Endpoints

Safety of the retreatment with PN40082 will be evaluated by the nature, severity, and frequency of treatment-emergent adverse events (TEAEs). All AEs that occur during the study will be recorded whether or not they are considered to be related to treatment. A description of the AE will be recorded with the date of onset, date of resolution, severity of the AE, relationship to the study device, action taken, and the outcome.

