5.2 Handling of Dropouts or Missing Data

All summaries will be generated using the available data without imputation for the missing values.

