7.1 Handling of Missing or Incomplete Dates for Adverse Events and Concomitant Medications

Adverse Events

Handling of partial dates is only considered for the start date. An adverse event with a partial start date is considered treatment emergent if:

- only the day is missing and the start month/year is the same or after the month/year of the first injection
- the day and month are missing and the start year is the same or greater than the year of the first injection date
- the start date is completely missing

Concomitant Medications

Handling of partial dates is only considered for the stop date. A medication with a partial stop date is considered concomitant if:

- only the day is missing and the stop month/year is the same or after the month/year of the first injection
- the day and month are missing and the stop year is the same or greater than the year of the first injection date
- the stop date is completely missing or the medication is ongoing.

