¹ Denominator is the number of TEAEs related to vascular injections/visual event reported by all subjects who received the corresponding treatment.

² Denominator for percentages by severity is the number of subjects with respective TEAEs after receiving the corresponding treatment. Numerator (count of subjects) is based on the rule that subjects reporting more than one same incidence associated with a treatment arm are counted only once for the treatment arm under the greatest reported severity.

Source: Listing 16.2.7.1.1

O:\Studies\Prollenium\SYM 2018-03\Biometrics\Programs\Tables\xxx.sas ran on Month Day, Year at hh:mm on data from Month Day, Year.

Table 14.3.2.8 – Duration of Most Frequently Occurring Treatment-Emergent Adverse Events (TEAEs) Related to Vascular Injections/Visual Events by MedDRA Preferred Term

Preferred Term	Treatment Group In PRO 2018-02	Events % (n/N) ¹	<7 Days % (n/N) ²	7-30 Days % (n/N) ²	>30 Days % (n/N) ²
Term 1	PN40082	0% (0/0)	0% (0/0)	0% (0/0)	0% (0/0)
	Restvlane Silk	0% (0/0)	0% (0/0)	0% (0/0)	0% (0/0)
	Total	0% (0/0)	0% (0/0)	0% (0/0)	0% (0/0)
Term 2	PN40082	0% (0/0)	0% (0/0)	0% (0/0)	0% (0/0)
	Restvlane Silk	0% (0/0)	0% (0/0)	0% (0/0)	0% (0/0)
	Total	0% (0/0)	0% (0/0)	0% (0/0)	0% (0/0)
...					
...					
...					

Most frequently occurring TEAEs related to vascular injections/visual event are those that were reported by 5% or more of the total retreated subjects.

¹ Denominator is the number of TEAEs related to vascular injections/visual event reported by all subjects who received the corresponding treatment.

² Denominator for percentages by severity is the number of subjects with respective TEAEs after receiving the corresponding treatment. Numerator (count of subjects) is based on the rule that subjects reporting more than one same incidence associated with a treatment arm are counted only once for the treatment arm under the longest duration.

Source: Listing 16.2.7.1.1

O:\Studies\Prollenium\SYM 2018-03\Biometrics\Programs\Tables\xxx.sas ran on Month Day, Year at hh:mm on data from Month Day, Year.

Table 14.3.2.9 – Overall Summary of Treatment-Emergent Adverse Events (TEAEs) Related to Vascular Injections/Visual Events

	PRO 2018-02 PN40082		PRO 2018-02 Restvlane Silk		Total	
	Subjects ¹ (N=xx)	Events ² (N=xx)	Subjects ¹ (N=xx)	Events ² (N=xx)	Subjects ¹ (N=xx)	Events ² (N=xx)
Overall	0 (0%)	0 (0%)	0 (0%)	0 (0%)	0 (0%)	0 (0%)
Duration						
Less than 1 week	0 (0%)	0 (0%)	0 (0%)	0 (0%)	0 (0%)	0 (0%)

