--------------	--------------	--------------------------------	-------------------	-------------------	-----------------------------	---------------------------	--------------------	----------------------------------	-------------------------------------	-----------

Investigator Ease of Use Assessment assess on the Numerical Rating Scale (NRS): 0 (Not Easy) to 10 (Most Easy).

O:\Studies\ Prollenium\SYM 2018-03\Biometrics\Programs\Listing\xxx.sas ran on Month Day Year at hh mm on data from Month Day, Year.

Listing 16.2.6.1 – Efficacy Evaluations of Lip Fullness Grading Scale and Perioral Lines at Rest Severity Scale

Site- Subject	Treatment in PRO 2018-02	Study Visit	Lip Fullness Grading Scale (LFGS) Rating				Perioral Lines at Rest Severity Scale (POL)			
			Overall Rating	Upper Lip Rating	Lower Lip Rating	Assessed by	Overall Rating	Upper Lip Rating	Lower Lip Rating	Assessed by
xx-xxx	R. Silk	Visit 1 (PRO 2018-02) Visit 1 (Retreatment)								

O:\Studies\ Prolenium\SYM 2018-03\Biometrics\Programs\Listing\xxx.sas ran on Month Day Year at hh mm on data from Month Day, Year.

Listing 16.2.6.2 – Efficacy Evaluations of Subject Satisfaction with Lips, Swelling and Global Aesthetic Improvement

Site- Subject	Treatment in PRO 2018-02	Study Visit	Subject Satisfaction with Lips VAS	Swelling Assessment		Patient Global Aesthetic Improvement (pGAI)	Investigator Global Aesthetic Improvement (iGAI)	
				Grade	Performed By		Score	Performed By

O:\Studies\ Prollenium\SYM 2018-03\Biometrics\Programs\Listing\xxx.sas ran on Month Day Year at hh mm on data from Month Day, Year.

Listing 16.2.7.1.1 – Adverse Events (Related to Vascular Injections/Visual Events)

Site-Subject	Trt. in PRO	FST	Reported by	System Organ Class// Preferred Term// Verbatim Term	Start Date Time [Day #]	Stop Date Time [Day #]	Severity Causality Outcome	Where on face Rel. to injection? Vision related?	Action Taken ¹	SAE
xx-xxx	R. Silk	III	Subj/Diary	GENERAL DISORDERS AND ADMINISTRATION SITE CONDITIONS// INJECTION SITE SWELLING// SWELLING ON FACE	01JAN2019 13:25 2	04JAN2019 08:30 5	MILD PROBABLY STABLIZED	QD1, QD3 Y N	3,4	N

Day # is calculated from baseline (Visit 1) date. Day 1 is the baseline date while Day -1 is the day prior to the baseline visit.

¹ Action Taken: 1=None, 2=Study treatment interrupted/discontinued, 3=Non-drug therapy, 4=New OTC or Rx drug added, 4=Hospitalized

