O:\Studies\ Prollenium\SYM 2018-03\Biometrics\Programs\Listing\xxx.sas ran on Month Day Year at hh mm on data from Month Day, Year.

Listing 16.2.7.1.2 – Adverse Events (Excluding Vascular Injections/Visual Events)

Site-Subject	Trt. in PRO	FST	Reported by	System Organ Class// Preferred Term// Verbatim Term	Start Date [Day #]	Stop Date [Day #]	Severity Causality Outcome	Where on face	Action Taken ¹	SAE
xx-xxx	R. Silk	III	Subj/Diary	NERVOUS SYSTEM DISORDERS// HEADACHE // HEADACHE	01JAN2019 2	04JAN2019 5	MILD UNLIKELY STABLIZED	QD1,QD3	1	N

Day # is calculated from baseline (Visit 1) date. Day 1 is the baseline date while Day -1 is the day prior to the baseline visit.

¹ Action Taken: 1=None, 2=Study treatment interrupted/discontinued, 3=Non-drug therapy, 4=New OTC or Rx drug added, 4=Hospitalized

O:\Studies\ Prolenium\SYM 2018-03\Biometrics\Programs\Listing\xxx.sas ran on Month Day Year at hh mm on data from Month Day, Year.

Note:

Repeat Listings 16.2.7.1.1 and 16.2.7.1.2 for AEs that led to study treatment interrupted/Discontinued and Serious AEs –

Listing 16.2.7.2.1 – Adverse Events (Related to Vascular Injections/Visual Events) Leading to Study Treatment Interrupted/Discontinued

Listing 16.2.7.2.2 – Adverse Events (Excluding Vascular Injections/Visual Events) Leading to Study Treatment Interrupted/Discontinued

Listing 16.2.7.3.1 – Serious Adverse Events (Related to Vascular Injections/Visual Events)

Listing 16.2.7.3.2 – Serious Adverse Events (Excluding Vascular Injections/Visual Events)

Listing 16.2.7.4 – Adverse Events (Related to Vascular Injections/Visual Events) Lasted more than 30 Days

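### The SAP has no duration rule for adverse events unresolved at last contact, so read literally its >30-day figures can only be understated

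*SAP*

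**What the plan says.** Three planned outputs depend on adverse-event duration:

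- **Table 14.3.2.8** splits the most frequent preferred terms into <7, 7-30 and >30 days. Its footnote says that subjects with repeat events of a term "are counted only once for the treatment arm under the longest duration". The denominator is every subject with that term.
- **Table 14.3.2.9** has three duration rows with the same cut-points, for subjects and for events.
- **Listing 16.2.7.4** is titled "Adverse Events (Related to Vascular Injections/Visual Events) Lasted more than 30 Days".

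The SAP gives no formula for duration. SAP 7.1 says of adverse-event dates: "Handling of partial dates is only considered for the start date". The bullets below that line serve only to decide whether an event is treatment-emergent. SAP 5.2 adds: "All summaries will be generated using the available data without imputation for the missing values". For medications, by contrast, SAP 7.1 covers the open-ended case: "the stop date is completely missing or the medication is ongoing".

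On data collection, Protocol 7.9.1 states: "A description of the AE will be recorded with the date of onset, date of resolution, severity of the AE", among other items. The outcome rows of Table 14.3.2.9 are Resolved, Improved, Stabilized, Worsened and Unchanged. Neither duration table has a row or column for ongoing or unknown duration.

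**The concern.** A duration needs two dates. The end date that the protocol collects is the date of resolution, and an event that has not resolved has none. With no rule for that case and no imputation, such an event has no duration to tabulate. Four of the five outcome rows describe something other than resolution, so the plan itself allows for these events.

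How long local reactions persist is a central safety question for a lip filler, and >30 days is the longest duration band that the SAP reports. Although these tables are titled for vascular-injection and visual events, their shells carry a summary row for injection-site or visual events. Ordinary local reactions therefore appear to fall within them. The companion tables for other events (the 14.3.3 series) report no duration at all. If the events left uncounted are the unresolved ones, the error has one direction.

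**Working it through.** The plan states no figure to reproduce. The check sets the rules side by side and then does the day arithmetic.

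**1. Follow one unresolved event through the rules.** Take onset on Day 2, with the event still present at the Month 6 call.
- Stop date: none, because the event has not resolved (Protocol 7.9.1).
- Rule for a missing stop date: none (SAP 7.1). Imputation: none (SAP 5.2).
- Table 14.3.2.8: the subject is in the denominator but in no duration column, so the row no longer adds to 100%.
- Table 14.3.2.9: the event is in the event denominator but in no duration row.
- Listing 16.2.7.4: the event has no computed duration with which to qualify.

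**2. Add a second event.** If the same subject also had a 3-day resolved event of that term, the longest computable duration is 3 days. Table 14.3.2.8 then places the subject in <7 days. This is misplacement rather than omission, and it also lowers the >30-day count.

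**3. Which unresolved events are already known to exceed 30 days?** Listing 16.2.1.2 counts study days as a difference plus 1. On that convention:

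minimum duration = last contact day − onset day + 1

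This exceeds 30 when onset day ≤ last contact day − 30.

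| Last contact | Latest onset for >30 days | Minimum duration if onset is Day 2 |
|---|---|---|
| Day 56 (window 52 to 60) | Day 26 (22 to 30) | 55 (51 to 59) |
| Day 168 (window 161 to 175) | Day 138 (131 to 145) | 167 (160 to 174) |

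For example, 168 − 138 + 1 = 31. An event that begins after Day 138 and is ongoing on Day 168 is not shown to exceed 30 days.

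**4. Size.** For one term, let k be the subjects affected, r those with an event resolved after more than 30 days, and u further subjects with an event unresolved more than 30 days after onset.

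- Literal reading: r/k
- Unresolved events counted: (r + u)/k
- Understatement: u/k

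The documents give no value for k, r or u, so the figures below are assumed counts, for illustration only. The protocol expects fewer than 158 subjects. Table 14.3.2.8 takes terms reported by at least 5% of retreated subjects, and 0.05 × 158 = 7.9, so k = 8 is the smallest qualifying total at that ceiling.

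| k | u = 0 | u = 1 | u = 2 | u = 4 |
|---|---|---|---|---|
| 8 | 0 | 12.5 points | 25 points | 50 points |
| 20 | 0 | 5 points | 10 points | 20 points |
| 40 | 0 | 2.5 points | 5 points | 10 points |

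One case in full: k = 20, r = 2, u = 2. The >30-day column shows 2/20 = 10% instead of 4/20 = 20%. If those two subjects had no other event of the term, the row adds to 18/20 = 90%.

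**The case against.** The strongest reply is that the exclusion is inferred. A reader might conclude that the SAP drops the longest-lasting events, but no sentence says so. The start-date rule in SAP 7.1 concerns treatment emergence, not duration. An event with onset on Day 2 that is recorded as present on Day 168 has been observed for more than 30 days, so counting it there arguably imputes nothing. SAP 6 calls the shells examples that may be changed during analysis, and other listing shells show an ongoing entry in the stop-date column. Follow-up of adverse events may continue past study end (Protocol 7.2), so some stop dates may arrive later.

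Unresolved events also stay visible in Listings 16.2.7.1.1 and 16.2.7.1.2 and in the outcome rows of Table 14.3.2.9. Swelling, texture, firmness and symmetry are tabulated by visit without needing a stop date. The study is descriptive, and no decision rule uses the >30-day count.

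All of this limits the point without removing it. A programmer could make the sensible choice, but nothing written requires it, and SAP 7.1 addresses open-ended records for medications while omitting them for events. The listings and outcome rows do not tabulate persistence by preferred term.

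Three further inferences should be resisted:
- The sample row in Listing 16.2.7.1.1 ("MILD PROBABLY STABLIZED", with a stop date on Day 5) might be taken as an error in the plan. It is dummy data and proves nothing either way.
- The follow-up wording in Protocol 7.3.3, "until the AE has resolved, become clinically insignificant, is stabilized, or the subject is lost to follow-up", might be read as a general rule. It applies only to subjects who withdraw because of an adverse event.
- It might be said that retreatment will look safer than it is. That holds only if unresolved events occur and are left uncounted, and other outputs would still show them.

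**Conclusion.** The gap is real and should be closed before database lock, although it does not put the study's conclusions in doubt by itself. Under the literal rules, the >30-day share for a term is too low by up to u/k, and never too high through this route. The size is unknown and is zero if every event resolves.

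The conclusion rests on two assumptions: that an unresolved event is recorded without a stop date, as collecting a date of resolution implies, and that the programmer applies SAP 7.1 and 5.2 as written.

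**What to change.** In SAP 7.1, and in the footnotes to Tables 14.3.2.8 and 14.3.2.9, state:

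1. Where a stop date is recorded, duration = stop date − start date + 1. Recorded stop dates are not overridden, whatever the outcome.
2. Where there is no stop date and the outcome is other than Resolved, minimum duration = last contact date − start date + 1. If this exceeds 30, the event counts in >30 days and appears in Listing 16.2.7.4. Otherwise it goes in a new category: ongoing at last contact, 30 days or less observed.
3. Where the outcome is Resolved but the stop date was not recorded, the event is shown as duration unknown. Treating it as ongoing could turn a brief bruise into a >30-day event.

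Last contact should mean the last visit or call at which event status was assessed. For subjects lost to follow-up, Protocol 7.2 ends participation at the date of the certified letter, which would inflate the minimum. Because Table 14.3.2.8 counts each subject once, its footnote should also give the order of precedence among the categories, with >30 days first.

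The cost is a few lines of text and one or two extra table categories. The visit and call dates are already in Listing 16.2.1.2, so no new data are needed. The >30-day figures may become slightly less favourable.

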7.2 Summary of Assessments

Visit Number (Month)	Visit 1 ^a	Phone Contacts	Visit 2 (Mo 1)	Visit 3 (Mo 2)	Phone Contact (Mo 6)	Unsched Visit
Scheduled Day(s)	Day 1	Day 3 & Day 14	Day 28	Day 56	Day 168	
Scheduling Window	± 7 days	± 2 days	± 2 days	± 4 days	± 7 days	
Informed consent	X					
Medical history/ demographics	X ^b					
Vital Signs	X					
Vision evaluations (Snellen visual acuity, confrontational visual fields, ocular motility) ^c	X		X	X		X ^d
Concomitant medication/ Treatment	X	X	X	X	X	X
Inclusion/exclusion criteria review	X					
Urine pregnancy test ^e	X					
Lip Fullness Grading Scale (LFGS) (overall, upper lip, and lower lip)	X		X	X		X ^d
Perioral lines at rest severity scale (POL) (overall, upper lip, and lower lip)	X		X	X		X ^d
Treatment with PN40082	X					
Investigator Ease of Use Assessment	X					
Patient GAI (pGAI)	X		X	X		X ^d
Swelling Assessment	X		X	X		X ^d
Investigator GAI (iGAI)	X		X	X		X ^d
Subject Satisfaction with Lips	X		X	X		X ^d
Lip function	X ^f		X	X		X ^d
Lip sensation	X ^f		X	X		X ^d
Lip texture	X ^f		X	X		X ^d
Lip firmness	X ^f		X	X		X ^d
Lip symmetry	X ^f		X	X		X ^d
Lip movement/function	X ^f		X	X		X ^d
Adverse event assessment	X	X	X	X	X	X
Subject Diary	Dispense		Collect			

Note: The timing of each visit is relative to Day 1, which is defined as the day the subject is treated.

- This is also Visit 5 of Protocol PRO 2018-02 and assessments performed at that visit do not need to be repeated.
- To be updated if/as needed for changes since Visit 1 of PRO 2018-02.
- To be performed prior to any treatment and repeated 30 minutes following any treatment and all follow-up visits.
- If/as needed
- For women of childbearing potential, to be completed prior to enrollment.
- To be performed prior to injections

Summary Tables

Table 14.1.2 – Subject Discontinuations by Reason for All Retreated Subjects

	PRO 2018-02 PN40082	PRO 2018-02 Restylane Silk	Total
Subjects Who Received Open-Label Treatment	0	0	0
Number Completed Study	0 (0%)	0 (0%)	0 (0%)
Total Discontinued	0 (0%)	0 (0%)	0 (0%)
Reason Discontinued			
-- Subject or legal representative withdrew consent	0 (0%)	0 (0%)	0 (0%)
-- Significant protocol violation	0 (0%)	0 (0%)	0 (0%)
-- Subject became pregnant	0 (0%)	0 (0%)	0 (0%)
-- An AE occurs for which the subject or the investigator determines that it is in the subject's best interest to be discontinued	0 (0%)	0 (0%)	0 (0%)
-- Lost to follow-up	0 (0%)	0 (0%)	0 (0%)
-- Investigator discretion	0 (0%)	0 (0%)	0 (0%)
-- Other	0 (0%)	0 (0%)	0 (0%)

Source: Listing 16.2.1.1

O:\Studies\Prolenium\SYM 2018-03\Biometrics\Programs\Tables\xxx.sas ran on Month Day, Year at hh:mm on data from Month, Day, Year.

Table 14.1.5 – Demographic Characteristics for Retreated Subjects

Parameter	Category	PRO 2018-02 PN40082 (N=xx)	PRO 2018-02 Restylane Silk (N=xx)	Total (N=xx)
Gender	Female	0 (0%)	0 (0%)	0 (0%)
	Male	0 (0%)	0 (0%)	0 (0%)
Ethnicity	Hispanic or Latino	0 (0%)	0 (0%)	0 (0%)
	Not Hispanic or Latino	0 (0%)	0 (0%)	0 (0%)
	Not Willing to Provide	0 (0%)	0 (0%)	0 (0%)
Race	White	0 (0%)	0 (0%)	0 (0%)
	Asian	0 (0%)	0 (0%)	0 (0%)
	Native Hawaiian or Other Pacific-Islander	0 (0%)	0 (0%)	0 (0%)
	Black or African American	0 (0%)	0 (0%)	0 (0%)
	American Indian or Alaska Native	0 (0%)	0 (0%)	0 (0%)
	Other	0 (0%)	0 (0%)	0 (0%)
	Mixed*	0 (0%)	0 (0%)	0 (0%)
Age (years)	N	0	0	0
	Mean ± SD	00.0 ± 00.00	00.0 ± 00.00	00.0 ± 00.00
	Median	0.0	0.0	0.0
	Min, Max	0, 0	0, 0	0, 0
Age Groups	18 to < 40	0 (0%)	0 (0%)	0 (0%)
	40 to < 64	0 (0%)	0 (0%)	0 (0%)
	64 to <75	0 (0%)	0 (0%)	0 (0%)
	>= 75	0 (0%)	0 (0%)	0 (0%)
Body Mass Index (BMI)**	N	0	0	0
	Mean ± SD	00.0 ± 00.00	00.0 ± 00.00	00.0 ± 00.00
	Median	0.0	0.0	0.0
	Min, Max	0.0, 0.0	0.0, 0.0	0.0, 0.0

Parameter	Category	PRO 2018-02 PN40082 (N=xx)	PRO 2018-02 Restylane Silk (N=xx)	Total (N=xx)
Fitzpatrick Skin Type	I	0 (0%)	0 (0%)	0 (0%)
	II	0 (0%)	0 (0%)	0 (0%)
	III	0 (0%)	0 (0%)	0 (0%)
	IV	0 (0%)	0 (0%)	0 (0%)
	V	0 (0%)	0 (0%)	0 (0%)
	VI	0 (0%)	0 (0%)	0 (0%)

*Subjects who reported more than one race are categorized as Mixed race.

** BMI = weight (lbs) / height² (in) x 703

Source: Listing 16.2.4.1, 16.2.4.6

O:\Studies\Prollenium\SYM 2018-03\Biometrics\Programs\Tables\xxx.sas ran on Month Day, Year at hh:mm on data from Month Day, Year.

Table 14.2.1 – Efficacy: Change from Baseline in Overall Lip Fullness Grading Scale (LFGS) at Visit 2/Month 1 and Visit 3/Month 2

Study Visit	Category	Statistics	PRO 2018-02 PN40082	PRO 2018-02 Restylane Silk	Total
Visit 1/Day 1 PRO 2018-02	Actual Value	N	0	0	0
		Mean ± SD	0.0 ± 0.00	0.0 ± 0.00	0.0 ± 0.00
		Median	0.0	0.0	0.0
		Min, Max	0, 0	0, 0	0, 0
Visit 1/Day 1 Retreatment	Actual Value	N	0	0	0
		Mean ± SD	0.0 ± 0.00	0.0 ± 0.00	0.0 ± 0.00
		Median	0.0	0.0	0.0
		Min, Max	0, 0	0, 0	0, 0
Visit 2/Month 1	Actual Value				
	...				
	Change from Visit 1 PRO 2018-02				
	...				
Visit 3/Month 2	Change from Visit 1 Retreatment				
	...				
	...				
	...				

LFGS: 0=Very Thin Lips, 1=Thin Lips, 2=Moderately Thick Lips, 3=Thick Lips, 4=Full Lips.

Source: Listing 16.2.6.1

O:\Studies\Prolenium\SYM 2018-03\Biometrics\Programs\Tables\xxx.sas ran on Month Day, Year at hh:mm on data from Month, Day, Year.

Note:

Table 14.2.1 will be used as the shell for the following table:

Table 14.2.2 – Efficacy: Change from Baseline in Overall Perioral Lines at Rest (POL) Severity Scale at Visit 2/Month 1 and Visit 3/Month 2

With first footnote changed to the following:

POL severity: 0=None, 1=Mild, 2=Moderate, 3=Severe.

Table 14.2.3 – Efficacy: Patient Global Aesthetic Improvement (pGAI) by Visit

Study Visit	Category	PRO 2018-02 PN40082	PRO 2018-02 Restylane Silk	Total
Visit 1/Day 1 Retreatment	N	0	0	0
	1 = Worse	0 (0%)	0 (0%)	0 (0%)
	2 = No Change	0 (0%)	0 (0%)	0 (0%)
	3 = Improved	0 (0%)	0 (0%)	0 (0%)
	4 = Much Improved	0 (0%)	0 (0%)	0 (0%)
	5 = Very Much Improved	0 (0%)	0 (0%)	0 (0%)
Visit 2/Month 1	...			
Visit 3/Month 2	...			

Source: Listing 16.2.6.2
O:\Studies\Prolenium\SYM 2018-03\Biometrics\Programs\Tables\xxx.sas ran on Month Day, Year at hh:mm on data from Month, Day, Year.

Note:

Table 14.2.3 will be used as the shell for the following table:

Table 14.2.4 – Efficacy: Investigator Global Aesthetic Improvement (iGAI) by Visit

Table 14.2.5 – Efficacy: Swelling Assessment by Visit

Study Visit	Category	PRO 2018-02 PN40082	PRO 2018-02 Restylane Silk	Total
Visit 1/Day 1 Retreatment	N	0	0	0
	0 = None	0 (0%)	0 (0%)	0 (0%)
	1 = Minimal	0 (0%)	0 (0%)	0 (0%)
	2 = Mild	0 (0%)	0 (0%)	0 (0%)
	3 = Moderate	0 (0%)	0 (0%)	0 (0%)
	4 = Severe	0 (0%)	0 (0%)	0 (0%)
Visit 2/Month 1	...			
Visit 3/Month 2	...			

Source: Listing 16.2.6.2

O:\Studies\Prolenium\SYM 2018-03\Biometrics\Programs\Tables\xxx.sas ran on Month Day, Year at hh:mm on data from Month, Day, Year.

Table 14.2.6 – Efficacy: Subject Satisfaction with Lips VAS by Visit

Study Visit	Statistics	PRO 2018-02 PN40082	PRO 2018-02 Restylane Silk	Total
Visit 1/Day 1 Retreatment	N	0	0	0
	Mean ± SD	0.0 ± 0.00	0.0 ± 0.00	0.0 ± 0.00
	Median	0.0	0.0	0.0
	Min, Max	0, 0	0, 0	0, 0
Visit 2/Month 1	...			
Visit 3/Month 2	...			

Source: Listing 16.2.6.2

O:\Studies\Prolenium\SYM 2018-03\Biometrics\Programs\Tables\xxx.sas ran on Month Day, Year at hh:mm on data from Month, Day, Year.

Table 14.3.1.1 – Exposure to Study Product and Investigator Ease of Use Assessment (Upper Lips) at Visit 1/Day 1 Retreatment

	Statistics	PRO 2018-02 PN40082	PRO 2018-02 Restylane Silk	Total
Amount of Syringe Used (ml)	N	0	0	0
	Mean ± SD	0.0 ± 0.00	0.0 ± 0.00	0.0 ± 0.00
	Median	0.0	0.0	0.0
	Min, Max	0, 0	0, 0	0, 0
Injection Techniques Used	N (%) Serial Puncture	0 (0.0%)	0 (0.0%)	0 (0.0%)
	N (%) Antegrade Linear Threading	0 (0.0%)	0 (0.0%)	0 (0.0%)
	N (%) Retrograde Linear Threading	0 (0.0%)	0 (0.0%)	0 (0.0%)
Depth of Injection	N (%) Submucosa	0 (0.0%)	0 (0.0%)	0 (0.0%)
	N (%) Intramuscular	0 (0.0%)	0 (0.0%)	0 (0.0%)
	N (%) Superficial Dermis	0 (0.0%)	0 (0.0%)	0 (0.0%)
	N (%) Mid Dermis	0 (0.0%)	0 (0.0%)	0 (0.0%)
	N (%) Deep Dermis	0 (0.0%)	0 (0.0%)	0 (0.0%)
	N (%) Subcutaneous Fat	0 (0.0%)	0 (0.0%)	0 (0.0%)
	Investigator Ease of Use Assessment	Mean ± SD	0.0 ± 0.00	0.0 ± 0.00
Median		0.0	0.0	0.0
Min, Max		0, 0	0, 0	0, 0

Investigator Ease of Use Assessment based on the Numerical Rating Scale (NRS): 0 (Not Easy) to 10 (Most Easy).

Source: Listing 16.2.5.1

O:\Studies\Prollenium\SYM 2018-03\Biometrics\Programs\Tables\xxx.sas ran on Month Day, Year at hh:mm on data from Month, Day, Year.

Note:

Table 14.3.1.1 will be used as the shell for the following table:

Table 14.3.1.2 – Exposure to Study Product and Investigator Ease of Use Assessment (Lower Lips) at Visit 1/Day 1 Retreatment

Table 14.3.1.3 – Exposure to Study Product and Investigator Ease of Use Assessment (Perioral Areas) at Visit 1/Day 1 Retreatment

Table 14.3.2.1 – Treatment-Emergent Adverse Events (TEAEs) Related to Vascular Injections/Visual Events by MedDRA System Organ Class and Preferred Term

System Organ Class Preferred Term	Reported by Subject or PI	PRO 2018-02	PRO 2018-02	Total (N=xx)
		PN40082 (N=xx)	Restylane Silk (N=xx)	
Subjects with at Least One Injection-Site or Visual TEAE	By Subject	0 (0%)	0 (0%)	0 (0%)
	By PI	0 (0%)	0 (0%)	0 (0%)
	Total	0 (0%)	0 (0%)	0 (0%)
Class 1	By Subject	0 (0%)	0 (0%)	0 (0%)
	By PI	0 (0%)	0 (0%)	0 (0%)
	Total	0 (0%)	0 (0%)	0 (0%)
Term 1	By Subject	0 (0%)	0 (0%)	0 (0%)
	By PI	0 (0%)	0 (0%)	0 (0%)
	Total	0 (0%)	0 (0%)	0 (0%)
...				
...				

Counts reflect numbers of subjects reporting one or more TEAE related to vascular injections/visual event that map to the MedDRA (version x x) system organ class/preferred term. At each level of summarization (system organ class or preferred term), subjects reporting more than one event are counted only once.

Source: Listing 16.2.7.1.1

O:\Studies\Prolenium\SYM 2018-03\Biometrics\Programs\Tables\xxx.sas ran on Month Day, Year at hh:mm on data from Month Day, Year.

Table 14.3.2.2 – Treatment-Emergent Adverse Events (TEAEs) Related to Vascular Injections/Visual Events by MedDRA System Organ Class, Preferred Term, and Severity

System Organ Class Preferred Term	Severity	PRO 2018-02 PN40082 (N=xx)	PRO 2018-02 Restylane Silk (N=xx)	Total (N=xx)
Subjects with at Least One Injection-Site or Visual TEAE	Mild	0 (0%)	0 (0%)	0 (0%)
	Moderate	0 (0%)	0 (0%)	0 (0%)
	Severe	0 (0%)	0 (0%)	0 (0%)
Class 1	Mild	0 (0%)	0 (0%)	0 (0%)
	Moderate	0 (0%)	0 (0%)	0 (0%)
	Severe	0 (0%)	0 (0%)	0 (0%)
Term 1	Mild	0 (0%)	0 (0%)	0 (0%)
	Moderate	0 (0%)	0 (0%)	0 (0%)
	Severe	0 (0%)	0 (0%)	0 (0%)
...				
...				

Counts reflect numbers of subjects reporting one or more TEAE related to vascular injections/visual event that map to the MedDRA (version x x) system organ class/preferred term. At each level of summarization (system organ class or preferred term), subjects reporting more than one event are counted only once (under the greatest reported severity).

Source: Listing 16.2.7.1.1

O:\Studies\Prolenium\SYM 2018-03\Biometrics\Programs\Tables\xxx.sas ran on Month Day, Year at hh:mm on data from Month Day, Year.

Table 14.3.2.3 – Treatment-Emergent Adverse Events (TEAEs) Related to Vascular Injections/Visual Events by MedDRA System Organ Class, Preferred Term, and Causality

System Organ Class Preferred Term	Causality	PRO 2018-02 PN40082 (N=xx)	PRO 2018-02 Restylane Silk (N=xx)	Total (N=xx)
Subjects with at Least One Injection-Site or Visual TEAE	Unlikely	0 (0%)	0 (0%)	0 (0%)
	Related*	0 (0%)	0 (0%)	0 (0%)
Class 1	Unlikely	0 (0%)	0 (0%)	0 (0%)
	Related*	0 (0%)	0 (0%)	0 (0%)
Term 1	Unlikely	0 (0%)	0 (0%)	0 (0%)
	Related*	0 (0%)	0 (0%)	0 (0%)
...				
...				

*Related category includes Possibly and Probably Related.

Counts reflect numbers of subjects reporting one or more TEAE related to vascular injections/visual event that map to the MedDRA (version x x) system organ class/preferred term. At each level of summarization (system organ class or preferred term) subjects reporting more than one event are only counted once (under the most likely relationship to study medication).

Source: Listing 16.2.7.1.1

O:\Studies\Prolenium\SYM 2018-03\Biometrics\Programs\Tables\xxx.sas ran on Month Day, Year at hh:mm on data from Month Day, Year.

Table 14.3.2.4 – Treatment-Emergent Adverse Events (TEAEs) Related to Vascular Injections/Visual Events by MedDRA System Organ Class, Preferred Term, and Number of Injections

System Organ Class Preferred Term	PRO 2018-02 PN40082		PRO 2018-02 Restvlane Silk	
	1 Injection (N=xx)	2 Injections (N=xx)	1 Injection (N=xx)	2 Injections (N=xx)
Class 1	0 (0%)	0 (0%)	0 (0%)	0 (0%)
Term 1	0 (0%)	0 (0%)	0 (0%)	0 (0%)
Term 2	0 (0%)	0 (0%)	0 (0%)	0 (0%)
Class 2	0 (0%)	0 (0%)	0 (0%)	0 (0%)
Term 1	0 (0%)	0 (0%)	0 (0%)	0 (0%)

...

Note: All retreated subjects received 1 more injection of PN40082 in this open-label study.
 Counts reflect numbers of subjects reporting one or more TEAE related to vascular injections/visual event that map to the MedDRA (version x x) system organ class/preferred term. At each level of summarization (system organ class or preferred term), subjects reporting more than one event are counted only once.
 Source: Listing 16.2.7.1.1
 O:\Studies\Prolenium\SYM 2018-03\Biometrics\Programs\Tables\xxx.sas ran on Month Day, Year at hh:mm on data from Month Day, Year.

Table 14.3.2.5 – Treatment-Emergent Adverse Events (TEAEs) Related to Vascular Injections/Visual Events by MedDRA System Organ Class, Preferred Term, and Fitzpatrick Skin Type (FST)

System Organ Class Preferred Term	Treatment Group In PRO 2018-02	FST I % (n/N) ¹	FST II % (n/N) ¹	FST III % (n/N) ¹	Pooled		FST V % (n/N) ¹	FST VI % (n/N) ¹	Pooled FST IV-VI % (n/N) ¹
					FST I-III % (n/N) ¹	FST IV % (n/N) ¹			
Subjects with at Least One Injection- Site or Visual TEAE	PN40082	0% (0/0)	0% (0/0)	0% (0/0)	0% (0/0)	0% (0/0)	0% (0/0)	0% (0/0)	0% (0/0)
	Restvlane Silk	0% (0/0)	0% (0/0)	0% (0/0)	0% (0/0)	0% (0/0)	0% (0/0)	0% (0/0)	0% (0/0)
	Total	0% (0/0)	0% (0/0)	0% (0/0)	0% (0/0)	0% (0/0)	0% (0/0)	0% (0/0)	0% (0/0)
Class 1	PN40082	0% (0/0)	0% (0/0)	0% (0/0)	0% (0/0)	0% (0/0)	0% (0/0)	0% (0/0)	0% (0/0)
	Restvlane Silk	0% (0/0)	0% (0/0)	0% (0/0)	0% (0/0)	0% (0/0)	0% (0/0)	0% (0/0)	0% (0/0)
	Total	0% (0/0)	0% (0/0)	0% (0/0)	0% (0/0)	0% (0/0)	0% (0/0)	0% (0/0)	0% (0/0)
Term 1	PN40082	0% (0/0)	0% (0/0)	0% (0/0)	0% (0/0)	0% (0/0)	0% (0/0)	0% (0/0)	0% (0/0)
	Restvlane Silk	0% (0/0)	0% (0/0)	0% (0/0)	0% (0/0)	0% (0/0)	0% (0/0)	0% (0/0)	0% (0/0)
	Total	0% (0/0)	0% (0/0)	0% (0/0)	0% (0/0)	0% (0/0)	0% (0/0)	0% (0/0)	0% (0/0)
...									
...									
...									

¹ N = number of subjects of a certain FST in the associated treatment group; n = number of subjects of a certain FST in the associated treatment group reporting TEAE. Counts reflect numbers of subjects reporting one or more TEAE related to vascular injections/visual event that map to the MedDRA (version x x) system organ class/preferred term. At each level of summarization (system organ class or preferred term), subjects reporting more than one event are counted only once.

Source: Listing 16.2.7.1.1

O:\Studies\Prolenium\SYM 2018-03\Biometrics\Programs\Tables\xxx.sas ran on Month Day, Year at hh:mm on data from Month Day, Year.

Table 14.3.2.6 – Most Frequently Occurring Treatment-Emergent Adverse Events (TEAEs) Related to Vascular Injections/Visual Events by MedDRA Preferred Term

System Organ Class Preferred Term	PRO 2018-02 PN40082 (N=xx)	PRO 2018-02 Restylane Silk (N=xx)	Total (N=xx)
Class 1			
Term 1	0 (0%)	0 (0%)	0 (0%)
Term 2	0 (0%)	0 (0%)	0 (0%)
Class 2			
Term 1	0 (0%)	0 (0%)	0 (0%)
...			
...			

Most frequently occurring TEAEs related to vascular injections/visual event are those that were reported by 5% or more of the total retreated subjects. Counts reflect numbers of subjects reporting one or more TEAE related to vascular injections/visual event that map to the MedDRA (version x x) system organ class/preferred term. At each level of summarization (preferred term) subjects reporting more than one event are only counted once.
 Source: Listing 16.2.7.1.1
 O:\Studies\Prollenium\SYM 2018-03\Biometrics\Programs\Tables\xxx.sas ran on Month Day, Year at hh:mm on data from Month Day, Year.

Table 14.3.2.7 – Severity of Most Frequently Occurring Treatment-Emergent Adverse Events (TEAEs) Related to Vascular Injections/Visual Events by MedDRA Preferred Term

Preferred Term	Treatment Group In PRO 2018-02	Events % (n/N) ¹	Mild % (n/N) ²	Moderate % (n/N) ²	Severe % (n/N) ²
Term 1	PN40082	0% (0/0)	0% (0/0)	0% (0/0)	0% (0/0)
	Restvlane Silk	0% (0/0)	0% (0/0)	0% (0/0)	0% (0/0)
	Total	0% (0/0)	0% (0/0)	0% (0/0)	0% (0/0)
Term 2	PN40082	0% (0/0)	0% (0/0)	0% (0/0)	0% (0/0)
	Restvlane Silk	0% (0/0)	0% (0/0)	0% (0/0)	0% (0/0)
	Total	0% (0/0)	0% (0/0)	0% (0/0)	0% (0/0)
...					
...					
...					

Most frequently occurring TEAEs related to vascular injections/visual event are those that were reported by 5% or more of the total retreated subjects.

¹ Denominator is the number of TEAEs related to vascular injections/visual event reported by all subjects who received the corresponding treatment.

² Denominator for percentages by severity is the number of subjects with respective TEAEs after receiving the corresponding treatment. Numerator (count of subjects) is based on the rule that subjects reporting more than one same incidence associated with a treatment arm are counted only once for the treatment arm under the greatest reported severity.

Source: Listing 16.2.7.1.1

O:\Studies\Prollenium\SYM 2018-03\Biometrics\Programs\Tables\xxx.sas ran on Month Day, Year at hh:mm on data from Month Day, Year.

Table 14.3.2.8 – Duration of Most Frequently Occurring Treatment-Emergent Adverse Events (TEAEs) Related to Vascular Injections/Visual Events by MedDRA Preferred Term

Preferred Term	Treatment Group In PRO 2018-02	Events % (n/N) ¹	<7 Days % (n/N) ²	7-30 Days % (n/N) ²	>30 Days % (n/N) ²
Term 1	PN40082	0% (0/0)	0% (0/0)	0% (0/0)	0% (0/0)
	Restvlane Silk	0% (0/0)	0% (0/0)	0% (0/0)	0% (0/0)
	Total	0% (0/0)	0% (0/0)	0% (0/0)	0% (0/0)
Term 2	PN40082	0% (0/0)	0% (0/0)	0% (0/0)	0% (0/0)
	Restvlane Silk	0% (0/0)	0% (0/0)	0% (0/0)	0% (0/0)
	Total	0% (0/0)	0% (0/0)	0% (0/0)	0% (0/0)
...					
...					
...					

Most frequently occurring TEAEs related to vascular injections/visual event are those that were reported by 5% or more of the total retreated subjects.

¹ Denominator is the number of TEAEs related to vascular injections/visual event reported by all subjects who received the corresponding treatment.

² Denominator for percentages by severity is the number of subjects with respective TEAEs after receiving the corresponding treatment. Numerator (count of subjects) is based on the rule that subjects reporting more than one same incidence associated with a treatment arm are counted only once for the treatment arm under the longest duration.

Source: Listing 16.2.7.1.1

O:\Studies\Prollenium\SYM 2018-03\Biometrics\Programs\Tables\xxx.sas ran on Month Day, Year at hh:mm on data from Month Day, Year.

Table 14.3.2.9 – Overall Summary of Treatment-Emergent Adverse Events (TEAEs) Related to Vascular Injections/Visual Events

	PRO 2018-02 PN40082		PRO 2018-02 Restvlane Silk		Total	
	Subjects ¹ (N=xx)	Events ² (N=xx)	Subjects ¹ (N=xx)	Events ² (N=xx)	Subjects ¹ (N=xx)	Events ² (N=xx)
Overall	0 (0%)	0 (0%)	0 (0%)	0 (0%)	0 (0%)	0 (0%)
Duration						
Less than 1 week	0 (0%)	0 (0%)	0 (0%)	0 (0%)	0 (0%)	0 (0%)
